9. TRIAL DESIGN

RETRIEVE AMI is an investigator-initiated, multi-centre, exploratory three arms, randomised controlled trial. Patients over the age of 18 admitted for primary PCI (pPCI) for ST elevation myocardial infarction and meeting the inclusion criteria laid out in section 10.2 will be 1:1:1 randomised to receive either standalone PCI (Arm 1), thrombus aspiration + PCI (Arm 2) or retriever thrombectomy + PCI (Arm 3). Recruitment is expected to last for 18 months with the study finishing when the last follow-up of the last recruited patient is completed and all data is entered into the study. Each participant is expected to remain in the study for 6 months during which one telephone follow-up at 6 months will be arranged. (Figure 1, Appendix A)

The RETRIEVE AMI will enrol specifically patients with

- evidence of large thrombus burden on coronary angiography
- with culprit lesion located in a relatively large caliber (diameter > 3.0 mm) coronary artery

By only including a large caliber vessel, the retriever-stent will be tested in a setting where the currently available technology is perceived to be suboptimal as described in section 6. Our decision to expand recruitment to the left coronary system was driven by our experience with the device in this trial as well as from published reports of the systematic evaluation of the NeVa (Vesalio) stent retriever device. Indeed, the authors have shown that thrombectomy is safe in both the left and right coronary artery systems.¹⁷ Procedurally, we are reducing the risk of a major interaction of the device by placing a coronary guidewire alongside the stent retriever allowing us to retain safe control of the vessel whilst the clot is retrieved.

[figure not shown]

Figure 1: Trial flow chart

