10.2. Inclusion Criteria

- Male or Female, aged 18-90 years.
- pPCI patient with ST elevation myocardial infarction.
- Angiographic criteria:
 - ◊ TIMI 0/1 flow at presentation
 - ◊ Angiographic thrombus score ≥ 4
 - ◊ Vessel diameter at site of occlusion ≥ 3.0 mm (measured by quantitative coronary angiography)

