11.4. Randomisation

Date and version No:22/04/2024 v4.0

Upon assent, participant will be randomised to one of the three study arms, by a system based on sealed envelopes. Randomization will take place in the cathlab once both inclusion and exclusion criteria are verified and assent provided.

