12.1.3. Investigational arm (Arm 3)

Participants randomised to the stent-retriever thrombectomy arm of the RETRIEVE AMI trial will undergo stent-retriever thrombectomy with the Solitaire™ X Revascularisation Device (Figure 3). The Solitaire™ X revascularisation device has been clinically approved and CE marked for use in acute ischaemic stroke endovascular intervention.¹⁴ Solitaire™ X works by mechanically retrieving the thrombus and restoring blood flow to the area distal to the occlusion. The Solitaire™ X Revascularisation Device is a self-expanding stent designed for dynamic clot integration with radiopaque markers that enhance visualisation of the optimal working length. Features including the range of stent diameters and usable lengths are presented in Appendix B. The device can be used in

vessels with a diameter between 2.0mm and 5.5mm at the thrombotic occlusion site (Appendix B).

Figure 3: Solitaire™ X device

After a thrombotic occlusion has been identified and crossed with a guidewire, the stent-retriever thrombectomy proceeds as described below (see Appendix C for schematic diagram).¹⁵ A microcatheter (e.g. PhenomTM, MarksmanTM) is advanced over the guidewire. Once the microcatheter has traversed the thrombotic occlusion the SolitaireTM X revascularisation device is advanced through the microcatheter until the usable length of the stent extends past each side of the thrombus in the vessel. Then the microcatheter is retracted to the proximal radiopaque marker of the stent. As this retraction occurs the stent self-expands and entangles the thrombus. Finally, the microcatheter and SolitaireTM X Revascularisation Device are withdrawn as a unit under continuous aspiration into the guide catheter. PCI will then proceed with devices and techniques driven by clinical decision making at the patient level and institutional level, and carried out in accordance with local guidelines.

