From a device perspective, in stroke patients Solitaire™ X revascularisation device failure was reported in one case (0.8%) in the two pivotal trials that examined this end-point with no significant sequelae.^{14,26} Regarding device related complications in patients randomised to the Solitaire™ X revascularisation device, arterial dissection or perforation was reported in 5/211 (2.3%). Perforations, albeit in the coronaries are encountered in routine PCI practice in 0.37% of patients²⁷, while edge dissections following stent deployment in 7.7% of patients.²⁸ The relatively higher perforation with the Solitaire™ X device can be explained by the tortuosity of the intracerebral vessels that are treated as well as the early stage of the thrombectomy experience in the RCTs and the small sample size. To minimise the potential for coronary perforations in our trial, we will include patients with thrombotic occlusions involving the right coronary artery prior to the crux, e.g. in a vessel segment with minimal, if any, tortuosity. Nonetheless, in the event of a coronary perforation the treatment – angioplasty – is similar to the definitive treatment for the myocardial infarction.

Finally, stroke in the context of pPCI is reported in 0.25% to 0.5% of STEMI cases²⁹⁻³¹ and in ~0.8% of STEMI patients with aspiration thrombectomy and PCI.³⁰ In the Solitaire™ X device trials, the rate of embolisation to vascular fields proximal to the target vessel is not reported. It is therefore not possible to estimate the risk of stroke for our trial. However, from a mechanistic perspective stent-retriever thrombectomy is based

Date and version No:22/04/2024 v4.0

on the concept of integration of the stent scaffold into the thrombus which in combination with the withdrawal of the stent into the microcatheter and the continuous aspiration on withdrawal renders embolisation of thrombotic material less likely.

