14.2. Analysis of Endpoints

In keeping with our usual practice, we will obtain expert statistical advice from the Centre for Statistics in Medicine (or equivalent) for each specific task. A flow diagram detailing number of participants screened and randomised will be provided. Analysis of the OCT-derived primary and secondary endpoints (including angiography-derived) will be conducted offline in a blinded fashion. Summary statistics, including means, medians, and variances, will be calculated at each time point and for each type of data and group (e.g. baseline characteristics, parameters derived from OCT, angiography-derived coronary physiology). The distribution of the levels will be described. For each parameter an analysis of variance will be carried out.

An analysis evaluating for a between group difference in pre-stent thrombus volume will first use an 1-way ANOVA with a 2-sided equality test to assess for an overall trend. Post-hoc analyses exploring the following hypotheses i) retriever thrombectomy (Arm 3) is different to no thrombus modification (arm 1) and ii) retriever thrombectomy (Arm 3) is different to aspiration thrombectomy (Arm 2) will be performed using the Dunnett test. Control of the Type I error at 5% two-sided significance level due to multiple testing will be achieved using Dunnett's method.³⁶ Missing data for the primary analysis will be dealt with complete case analysis if data missingness is <10% (<3 cases per group). If missingness is higher, multiple imputation will be performed instead. Major adverse cardiac and cerebrovascular events will be analysed using proportions statistical testing (Fisher's exact or χ^2 tests), yet they represent an exploratory analysis.

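### Recruitment was widened to the left coronary system mid-trial, but safety is reported only by arm and the primary comparison does not use culprit artery

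*Combined protocol and SAP*

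**What the plan says.** **Eligibility.** Section 9 (Trial Design) says: "Our decision to expand recruitment to the left coronary system was driven by our experience with the device in this trial". Its second ground is "published reports of the systematic evaluation of the NeVa (Vesalio) stent retriever device", from which it concludes that "the authors have shown that thrombectomy is safe in both the left and right coronary artery systems". The device under test is another one: Section 12.1.3 says that Arm 3 patients "will undergo stent-retriever thrombectomy with the Solitaire™ X Revascularisation Device". Section 10.2 names no artery; its anatomical criterion is "Vessel diameter at site of occlusion ≥ 3.0 mm (measured by quantitative coronary angiography". Section 12.2, explaining how the perforation risk will be kept low, still says "we will include patients with thrombotic occlusions involving the right coronary artery prior to the crux".

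**Timing.** The synopsis gives a planned start of 01/03/2022. Appendix D lists a change to the eligibility criteria on 21/12/2022 and an added site on 02/10/2023. It does not say which amendment admitted left-sided culprits.

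**Randomisation.** Section 11.4: "participant will be randomised to one of the three study arms, by a system based on sealed envelopes". Neither this section nor Section 11.3 describes stratification.

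**Analysis.** Section 14.2: "An analysis evaluating for a between group difference in pre-stent thrombus volume will first use an 1-way ANOVA", followed by Dunnett comparisons of Arm 3 with Arm 1 and with Arm 2. No covariate is named. Summaries are planned by time point, data type and group. The halt-rule counts (Sections 13.6 and 14.3) and MACCE (Section 14.2) are not split by artery either.

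**The concern.** Safety of retriever thrombectomy is a co-primary objective of a device pilot, and the device is used outside its licence (Section 12.2). The protocol itself treats artery as relevant to safety, because Section 12.2 ties perforation risk to a right coronary segment with little tortuosity. Left-sided vessels are therefore the newer and less supported part of the population. The published evidence cited for them concerns another device, and any in-trial experience gathered before the widening would come from the population eligible at that time.

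If results are shown only by arm, a clean safety record could rest mainly on right coronary patients and still be read as covering both systems. For efficacy, culprit artery is known before randomisation. If it is related to thrombus volume, leaving it out of the model gives away precision and lets a chance imbalance between small arms move the estimate.

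**Working it through.** **1. Passages side by side**

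| Section | Population described |
|---|---|
| 9 | recruitment expanded to the left coronary system |
| 10.2 | diameter, flow and thrombus score; no artery named |
| 12.2 | right coronary artery before the crux, as a measure against perforation |

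The statement in 12.2 works as risk reduction only if it restricts entry. Sections 9 and 10.2 contain no such restriction, so the three do not agree.

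**2. What zero events would show**

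With 0 events in n patients, the one-sided 95% upper bound is 1 − 0.05^(1/n).

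- All of Arm 3, n = 27 (Section 14.1): 1 − 0.05^(1/27) = 10.5%.
- Left-artery patients in Arm 3: the documents give no share. Assuming 30-50%, 27 × 0.3 = 8.1 and 27 × 0.5 = 13.5, so about 8 to 13 patients.
- n = 13: 1 − 0.05^(1/13) = 20.6%. n = 8: 1 − 0.05^(1/8) = 31.2%.

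The left-artery bound is two to three times the pooled one. If recruits before the widening were right coronary only, the whole-trial left share is lower than the share after it, and the left-artery bound is wider.

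**3. The plan's own power figure**

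Inputs from Section 14.1: mean 9.6 mm³, SD 5.1 mm³, 33% reduction, 24 evaluable per arm, stated power 80%.

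- Target difference: 0.33 × 9.6 = 3.168 mm³.
- Standard error of a contrast: 5.1 × √(2/24) = 1.472 mm³.
- Power, two-sided 0.05, normal approximation: Φ(3.168/1.472 − 1.96) = Φ(0.192) = 57.6%.

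The stated 80% does not reproduce: the same inputs need 2 × (1.96 + 0.842)² × 5.1²/3.168² = 40.7, or 41 per arm. That is a separate matter. Here 57.6% is only the baseline for the gain from adjustment. It makes no allowance for two comparisons; with the Dunnett critical value it is 46%.

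**4. Gain from adjusting for artery**

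Assume 40% left culprits and a difference D in mean volume between arteries, with the total SD held at 5.1. The share of variance removed is 0.4 × 0.6 × D²/5.1².

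| D (assumed) | Variance removed | Residual SD | SE | Nominal power |
|---|---|---|---|---|
| 2 mm³ | 0.24 × 4/26.01 = 3.7% | 5.00 | 1.445 | Φ(2.193 − 1.96) = 59% |
| 4 mm³ | 0.24 × 16/26.01 = 14.8% | 4.71 | 1.359 | Φ(2.331 − 1.96) = 64% |

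If D = 0, nothing is gained and one degree of freedom is spent.

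**5. Chance imbalance**

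Without stratification, the difference in left share between two arms of 24 has SD √(2p(1−p)/24): 13 points at p = 0.3 and 14 points at p = 0.5. A 20-point gap would shift the contrast by 0.2 × D, that is 0.4 mm³ (D = 2) to 0.8 mm³ (D = 4). Against the standard error of 1.472 mm³ this is 0.27 to 0.54 standard errors.

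**6. Why efficacy by artery can only be descriptive**

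Even at a 50:50 split (12 per arm in each artery), the 95% half-width for a contrast within one artery is 1.96 × 5.1 × √(2/12) = 4.1 mm³, wider than the 3.168 mm³ target. The artery-by-treatment interaction detectable with 80% power is 2.80 × 5.1 × √(4/12) = 8.2 mm³, close to the whole control mean.

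**The case against.** The widening changed entry for three arms randomised concurrently 1:1:1, so it does not by itself bias the contrast or inflate the type I error. Chance imbalance in a covariate is already allowed for in the standard error, and the shifts in step 5 lie well inside it; the unadjusted test is valid. All of this stands.

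A reader might infer more from the reference to in-trial experience in an unmasked trial, namely that outcomes by arm prompted the widening. The documents do not say so. Experience with the device may mean handling or deliverability, and although treatment is unmasked, Section 14.2 has the OCT and angiographic endpoints analysed blinded.

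The artery share and the difference between arteries are assumptions, and the protocol gives no sign that thrombus volume differs by artery once its diameter, flow and thrombus-score criteria are met. That also stands, so the precision gain may be nil. Section 9 names NeVa openly, so readers can already see that the published series used another device.

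Finally, the plan is silent on results by artery and does not rule them out, the trial is labelled an exploratory pilot, and a safety group reviews all serious events cumulatively. This lowers the severity. But reporting left to choice after the data are seen is weaker than reporting fixed beforehand, and the safety group's review does not give readers denominators. Counts in 8 to 13 patients cannot establish left-coronary safety; they would show how little has been tested.

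**Conclusion.** The point holds as one of interpretability and precision, not of validity. Two things follow from the text alone: Sections 9, 10.2 and 12.2 describe different populations, and nothing in the plan obliges the report to show how many left-coronary patients received the device or what happened to them. On an assumed 30-50% left share, a pooled bound of 10.5% after zero events would stand where the left-artery bound is 21-31%.

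The case for the covariate is weaker: nominal power of 59-64% against 58%, resting on an assumed 40% left share and a 2-4 mm³ difference between arteries. It is worth having because it costs almost nothing.

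The documents do not support a claim that the widening was driven by results by arm, or that it makes the primary comparison invalid. A before-and-after split of the primary result is not needed either: it would mix artery with other eligibility changes and possibly with the added site.

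**What to change.** Before any comparison by arm is made:

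1. **Safety tables.** In Section 14.2, commit to reporting device-related target vessel complications, device deficiency, the event types counted in Section 13.6, and MACCE by culprit artery (right v left) within arm. Give the number treated in each cell and label the results descriptive.
2. **Primary contrasts.** Include culprit artery as a fixed covariate in the Arm 3 v Arm 1 and Arm 3 v Arm 2 comparisons, keeping the Dunnett adjustment. It is known for every arm from the eligibility angiogram taken before randomisation (Section 11.6, Stage 1).
3. **Text.** Reconcile Sections 9, 10.2 and 12.2 on which arteries are eligible and on what the perforation-risk argument rests. Which statement is right is for the sponsor to decide.

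The cost is analysis wording, additional table rows and one degree of freedom. No extra patients or procedures are needed. By-artery estimates will be imprecise and should be presented with intervals and without tests.

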10. PARTICIPANT IDENTIFICATION

10.1. Trial Participants

Patients over 18 years of age having pPCI for ST elevation myocardial infarction and meeting the inclusion criteria as listed below will be randomised to either retriever thrombectomy + PCI, or thrombus aspiration + PCI, or standalone PCI.

10.2. Inclusion Criteria

- Male or Female, aged 18-90 years.
- pPCI patient with ST elevation myocardial infarction.
- Angiographic criteria:
 - ◊ TIMI 0/1 flow at presentation
 - ◊ Angiographic thrombus score ≥ 4
 - ◊ Vessel diameter at site of occlusion ≥ 3.0 mm (measured by quantitative coronary angiography)

10.3. Exclusion Criteria

The participant may not enter the trial if ANY of the following apply:

- Female participant who is pregnant or lactating
- Participant with known hypersensitivity to nickel-titanium
- Unconscious at presentation
- Late presenter (pain to wire time > 12 h)
- Class Killip III/IV and/or profound bradycardia (HR < 40 bpm)
- Known history of kidney failure
- Ostial occlusion

- Highly tortuous vessel*
- Highly calcified vessel
- Suspected (angiographically) spontaneous coronary artery dissection
- Stent thrombosis
- Previous stent implanted proximal to the occlusion site
- Previous CABG
- Previous STEMI/TIA/Stroke
- Known anaemia (Hb <9).

*A highly tortuous vessel is defined by the presence of ≥ 3 consecutive curvatures of 90° to 180° measured at end-diastole in a major epicardial coronary artery ≥ 2 mm in diameter.¹⁸ In our protocol tortuosity will lead to a participant's exclusion if it is affecting the vessel at the target lesion or proximal to it.

11. TRIAL PROCEDURES

11.1. Informed Consent

Informed consent will be obtained, with the recruitment approach to the patient, as described below.

11.1.1. Waiver request for patients having emergency angioplasty procedure

The clinical treatment of these patients is in the emergency context and delays to treatment are detrimental. It is necessary to administer prompt emergency treatment and it is not always possible to identify and approach a Consultee beforehand. Thus we would seek a waiver, as described in Section 32(9) of the Mental Capacity Act, since

- a) the treatment needs to be given urgently,
- b) it is necessary to take the action for the purpose of the research urgently,

but

- c) it is not reasonably practicable to consult prior to enrolling the patient.

In this situation the Mental Capacity Act allows the participant to be enrolled with an agreement of a registered medical practitioner (RMP) not involved in the research or in accordance with a procedure agreed with the appropriate body (i.e. REC). Since this is only applicable for the duration of the emergency we will seek written informed consent as soon as reasonably practicable (see diagram and Section 11.1.1.2 below). This process includes an important role for a healthcare professional as a type of patient "advocate". This is discussed in section 11.1.1.2 below. We also seek approval from the REC for the waiver procedure.

11.1.1.1. Verbal assent

Because of the urgency of the situation it is not feasible to obtain fully informed written consent. Fully informed consent requires that the potential participant have time to read and reflect on a patient information sheet which in this context is clinically inadvisable. We therefore propose to obtain verbal assent so as to optimize the amount of appropriate information conveyed to potential participants

acutely and minimize the clinical risks involved with substantial delay. The research study will be discussed verbally with the patient and the risks and benefits explained.

In detail the patient at the time of verbal assent process will be informed that the particular pattern of heart attack they are having would be suitable for recruitment in our research trial which investigates a new device to remove the blood clot that is causing the heart attack. We will explain that as part of the trial they will receive either standard of care procedures or the investigational device. We will also briefly mention that we will be obtaining some extra pictures from within the arteries, a sample of the clot and measurements of flow and resistance in the small net of capillaries feeding the heart.

Participants will be reminded that they have the right to withdraw from the study at any stage and that this will not affect their treatment or human rights. The research and clinical team have extensive experience of patient assent, and the role of a Patient Advocate (see below), through the recruitment of approximately 500 participants undergoing emergency PCI for STEMI in the OxAMI [Ethics Ref 11/SC0397] and OxAMI PICSO [Ethics Ref 15/SC0167] studies. Newcastle upon Tyne Hospitals NHS Foundation Trust is a participating site to the OxAMI Study.

Only conscious patients, able to provide verbal assent will be enrolled in the study.

Commented [GS(O1]: I don't think this is needed here?

Commented [RK2R1]: It is as the assent relies on OxAMI advocates.

11.1.1.2. Patient Advocate

Because of the urgency of the situation it is not feasible to obtain written informed consent from the patient prior to enrolment, so an RMP or patient "advocate" will be identified to act in accordance with section 32(9). The Patient Advocate will act as witness and documenter of the verbal assent process for all conscious potential participants and/or overseer of the waiver process as a whole. This RMP will be present at the time of emergency treatment, but is not part of the research team. The Advocate will ensure that the verbal assent process is undertaken, that the patient does not object (i.e. the patient "assents" rather than "dissents"), and that the researcher has taken practical steps to explain the study, risks and benefits, within the context of the emergency clinical situation, and in accordance with the clinical status of the patient. The Advocate in this situation will be a healthcare professional such as a

specialist nurse. Assessment of patients in this context is within their professional capacity and the role here will be to witness verbal assent.

Most of the nursing staff at the Oxford Heart Centre has already attended a series of seminars to make them aware of their specific roles and responsibilities in this situation, and they have acted as patients' advocates through the recruitment of approximately 500 participants undergoing emergency PCI for STEMI in the ongoing OxAMI and OxAMI PICSO studies. The seminars have been directed by an ethicist who is not directly involved with the research project. We will continue to provide this training and draw on the extensive experience of the members of the clinical team currently acting as a Patient Advocate. Staff training at the Newcastle upon Tyne University Hospitals NHS Foundation Trust is ongoing.

[figure not shown]

Figure 2: Informed consent in emergency research

